### ***Intervention Groups***

**Postural Education (PE) Group.** Immediately after baseline posture assessment, PE group members received a one-time 20-minute in-person one-on-one standardized educational session by a research team member in the laboratory. Topics included health risks associated with forward head posture (Bayattork et al. 2019; Cuellar & Lanman 2017; Kalichman et al. 2016; Hansraj 2014; Lau et al. 2010); postural guidelines for using mobile electronic devices (Abdelhameed & Abdel-aziem 2016; Gustaffson 2012; Syamala et al. 2018), desktop computers (NIH 2021), laptop computers (NIH 2021; Sahu et al. 2021), and rest break guidelines (Kim & Koo 2016; Neupane et al. 2017; Vate-U-Lan 2015; Kar & Hedge 2020; Carter et al. 2018; Engelmann et al. 2011). At the conclusion of the educational session, each PE group participant was emailed a copy of the presented educational information and guidelines. A weekly email was sent to group members during the 4-week intervention period to provide reminders and encouragement to adhere to postural guidelines. Participants were asked not to begin any new exercise program or alter their current physical activity level over the next four weeks.

**Self-Myofascial Release + Stretching (SMRS) Group.** Immediately after baseline posture assessment, SMRS group members received a 15-minute in-person one-on-one standardized instructional/training session for the SMRS intervention provided by a research team member in the laboratory. A 12 x 6 x 6 inch high-density myofascial roller (NASM Tool, Cygnet Systems, Dallas, TX) and a 23-inch soft-tissue mobilization tool (STMT) (Therapist's Choice® Pressure Point Hook Cane, Tampa, FL) was provided at no cost to group members to enable implementation of a 4-week home program. Implemented protocols followed the National Academy of Sports Medicine (NASM) recommendations for inhibitory and lengthening techniques (Fahmy 2022). Participants were instructed to apply self-myofascial release (SMR) to the thoracic spine (TS) using the myofascial roller by holding pressure over the central region of

the TS for 30 seconds, followed by six repetitions of active rolling up and down the length of the TS (up + down equaling 1 repetition) over a 90 second time period to promote mobilization of restricted myofascial tissues and restoration of upright posture (Fahmy 2022). Participants were asked to apply SMR to the center of the muscle belly in bilateral sternocleidomastoid (SCM) and upper cervical extensor (UCE) muscles using self-applied pressure with fingertips, while the STMT was utilized to administer SMR to center of the muscle belly in bilateral upper trapezius (UT) muscle and pectoralis minor (PM) muscle for 30 seconds (Fahmy 2022). For the first two weeks of the study, participants performed SMR three times per week on non-consecutive days. During weeks three and four, participants were instructed to progress SMR protocol frequency to five days per week. They were also instructed to perform static stretching to bilateral SCM, UT, PM, and UCE muscles after SMR on three non-consecutive days per week. During the first two weeks of the study, subjects performed two repetitions of stretches held for 20 seconds, and progressed to three repetitions of 30 seconds, five days per week during weeks three and four. At the conclusion of the training session, each group participant was emailed a copy of instructions for the assigned intervention. A weekly reminder email was sent to group members during the 4-week intervention period to encourage corrective exercise program (CEP) adherence. Participants were asked not to begin a new exercise program other than their assigned CEP or alter their current physical activity level during the 4-week intervention period.

**Self-Myofascial Release + Stretching + Strengthening (SMRSS) Group.** Immediately after baseline posture assessment, SMRSS group members received a 20-minute in-person one-on-one standardized instructional/training session provided by a research team member in the laboratory that included the same SMR + stretching protocol as the SMRS group, as well as incorporated strengthening exercises following NASM recommendations for activation and

integration techniques (Fahmy 2022). Group participants received a 12 x 6 x 6 inch high-density myofascial roller (NASM Tool, Cygnet Systems, Dallas, TX), a 23-inch soft-tissue mobilization tool (Therapist's Choice® Pressure Point Hook Cane, Tampa, FL), a 36 inch medium resistance (resistance = 20 lb.) exercise tube with handles (Stroops, model: Slastix Toner, Clearfield, UT), and a 36-inch medium resistance (resistance = 3.7-5.5 lbs.) exercise band (Theraband, Akron, OH) at no cost to enable implementation of the prescribed 4-week home program. Strengthening exercises included the supine chin tuck (SCT), upper thoracic-lower cervical extension (UTLCE), and a single-arm row with trunk rotation (SARTR). The SCT was performed progressed in three phases: Week 1: chin tuck held 2 seconds, 4 second return to start position, repeated five times. Week 2: same as week 1, but incorporated a towel roll placed behind head to enable increased range of motion during the exercise. Week 3 and 4: chin tuck with head lift 1 inch above the towel roll was held for 2 seconds, 4 second return to start position, repeated five times. The UTLCE exercise was performed by placing the resistive exercise band around the back of the head with neck flexed 15-20 degrees. Participants were instructed to extend their neck to a neutral position against the resistance of the band and hold for 2 seconds, followed by a 4 second return to start position. The SARTR exercise was performed by placing one foot forward; completing a single arm row with exercise tubing using the contralateral arm compared to the lead leg; rotating the trunk 90 degrees toward the side of the body performing the row; followed by reversing these movements to return back to start position in a controlled manner. This exercise was performed on both the right and left sides. The UTLCE and SARTR exercises were performed with 1 set of 10 repetitions for weeks 1-2 and progressed to 2 sets of 10 repetitions in weeks 3-4 (Fahmy 2022). Participants were asked to perform all muscle strengthening exercises three times per week on non-consecutive days throughout the 4-week

intervention period. At the conclusion of the training session, each group participant was emailed a copy of instructions for the assigned intervention. A weekly reminder email was sent to group members during the 4-week intervention period to encourage corrective exercise program (CEP) adherence. Participants were asked not to begin a new exercise program other than their assigned CEP or alter their current physical activity level during the 4-week intervention period.

**Control Group (CG).** Immediately after baseline CVA assessment, participants randomly assigned to the CG were informed they would not be receiving an intervention and were asked not to begin any new exercise program or alter their current physical activity level over the next four weeks.

### ***Questionnaires and Follow-up Posture Assessment***

Two weeks into the study, participants assigned to intervention groups completed a mid-study questionnaire to assess intervention compliance. After the completion of 4-week intervention period, participants in the intervention groups completed a post-study questionnaire to assess intervention compliance and participants in all groups were asked to return to the Biomechanics laboratory to undergo a follow-up posture assessment.

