between the intersection of two lines: the first line drawn from the tragus of the ear to the spinous process of C7 vertebrae and the second line drawn horizontally through C7 spinous process (Kim et al. 2016). A second researcher directly observed the PI perform each CVA assessment, as well as provided verbal agreement with the accuracy of angle measurement. For each participant, the CVA was derived by taking the mean of two CVA measurements that were assessed on the captured photographs (Kim et al. 2016).

Inclusion criteria included completion of informed consent, craniovertebral angle  $\leq 53$  degrees (Lee et al. 2017) and self-rating of Transtheoretical Model stage of change stage  $\geq 3/5$  on a questionnaire to indicate their readiness to comply with an assigned exercise prescription or postural guidelines (Kuroda et al. 2012). Exclusion criteria consisted of any musculoskeletal injury to the head, shoulders, or spine within the last six months; diagnosis of pathology related to the cervical spine, thoracic spine, or upper extremities; or non-clearance for physical activity based on results of the PAR-Q+ questionnaire. A total of 79 participants met inclusion criteria and were included in the study.

Randomization of participant group assignments was completed by the PI using a block randomization generator on a website (<http://www.randomization.com>). Utilizing a sequence created by the block randomizer, the PI placed participants who met inclusion criteria into one of four groups: (PE; n = 20), self-myofascial release + stretching (SMRS; n = 20), self-myofascial release + stretching + strengthening (SMRSS; n = 19), and control group (CG; n = 20). A hard-copy of the sequence generator report was kept concealed in a manila folder and was only opened by the PI during group delegation. Participants and researchers were not blinded to group assignment.

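### No systematic collection of pain, injury or other harm is described in any arm after randomisation, although 39 people were assigned a home neck and shoulder programme that steps up mainly after week 2

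*Combined protocol and SAP*

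**What the plan says.** Injury is asked about once, at screening. The Study Protocol section excludes people with "any musculoskeletal injury to the head, shoulders, or spine within the last six months", people with diagnosed cervical, thoracic or upper-extremity pathology, and people not cleared by the PAR-Q+.

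After randomisation, the combined document describes these contacts:

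- **Week 2** (Questionnaires and Follow-up Posture Assessment): "participants assigned to intervention groups completed a mid-study questionnaire to assess intervention compliance".
- **After week 4, questionnaire** (same section): "participants in the intervention groups completed a post-study questionnaire to assess intervention compliance".
- **After week 4, visit** (same section): "participants in all groups were asked to return to the Biomechanics laboratory to undergo a follow-up posture assessment".
- **Emails, postural education arm** (Intervention Groups): "A weekly email was sent to group members during the 4-week intervention period to provide reminders and encouragement".
- **Emails, both exercise arms** (Intervention Groups): "A weekly reminder email was sent to group members during the 4-week intervention period to encourage corrective exercise program (CEP) adherence".
- **Control arm** (Intervention Groups): no contact is described between baseline and the follow-up visit.

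The exercise programmes are done at home after one training session. They become heavier from week 3. Stretching "progressed to three repetitions of 30 seconds, five days per week during weeks three and four", and in the strengthening arm the neck extension and row exercises "progressed to 2 sets of 10 repetitions in weeks 3-4".

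Statistical Analysis names no harm outcome. Results gives none, and gives no arm or reason for those who did not complete.

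**The concern.** The two exercise arms apply pressure to neck, shoulder and chest muscles and stretch them, and one arm adds resisted neck extension. All of this is self-administered. The mid-study questionnaire falls just before the main increase in load, when a question about symptoms would be most useful, but its only stated purpose is compliance.

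Three things are at stake. First, the trial can report benefit on CVA with nothing to set against it, and the silence of Results on harm gives no reassurance, because no enquiry is described. Second, a participant who cut back or stopped because of pain could not be told apart from one who lost interest. Third, controls get no questionnaire at all, so even a symptom volunteered on a compliance form would have no counterpart in the control arm.

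**Working it through.** The documents give no safety figure, so there is none to reproduce. The check has four parts.

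**1. Contacts set side by side.** For each contact: who receives it, and what it is described as recording.

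- Week-2 questionnaire: three intervention arms; compliance.
- End-of-study questionnaire: three intervention arms; compliance.
- Weekly emails: three intervention arms; outgoing reminders, no data described.
- Follow-up visit: all four arms; posture.
- Control arm before follow-up: nothing described.

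No row records symptoms or injury.

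**2. Load before and after week 2** (Intervention Groups).

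- Stretching, per muscle and side: 2 × 20 s × 3 days = 120 s/week in weeks 1-2; 3 × 30 s × 5 days = 450 s/week in weeks 3-4; ratio 450/120 = 3.75.
- Self-myofascial release: 3 to 5 days/week; ratio 5/3 = 1.67.
- Neck extension and row (row counted per side): 10 × 3 = 30 repetitions/week, then 20 × 3 = 60; ratio 2.
- Chin tuck: five repetitions throughout, but made harder at week 2 and again at week 3.

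Week 2 is therefore the main step, not the only one. These ratios describe exposure, not harm.

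**3. Numbers exposed and lost.** Study Protocol gives 20 + 20 + 19 + 20 = 79 randomised, of whom 20 + 19 = 39 were in the exercise arms. Results gives 51 + 21 = 72 completers. Losses: 79 − 72 = 7, and 7/79 = 8.9%.

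**4. What asking could have shown.** The event rates below are assumptions; the documents give none.

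Chance of at least one event, 1 − (1 − p)^n:

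- p = 2%: 54.5% with n = 39; 31.9% with n = 19 (strengthening arm alone).
- p = 5%: 86.5%; 62.3%.
- p = 10%: 98.4%; 86.5%.

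One-sided 95% upper limit if everyone was asked and no event found, 1 − 0.05^(1/n):

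- n = 39: 7.4%.
- n = 19: 14.6%.
- If all seven losses came from the exercise arms and went unasked, n = 32: 1 − 0.05^(1/32) = 8.9%. If all came from the strengthening arm, n = 12: 1 − 0.05^(1/12) = 22.1%.

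Power for 39 exercise against 20 control participants (two-sided 0.05, normal approximation):

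- 10% v 2%: about 15%.
- 20% v 5%: about 30%.
- 30% v 5%: about 63%.

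A common item would therefore pick up and describe frequent harms. It would not support a well-powered comparison between arms.

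**The case against.** The strongest reply is that this is a short summary and its silence is not proof. The questionnaires themselves are not in the document; only their purpose is stated. Participants could have reported a problem unprompted. The document makes no claim of safety or tolerability, so no stated result is overturned. Every participant in the exercise arms reported adherence in at least the 50-75% band on both questionnaires, which does not suggest widespread stopping because of pain. The trial is also finished, so new items at week 2 cannot help it.

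Much of this stands, and it rules out several stronger readings that a reader might infer:

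- *That no harm was recorded, or that none could have come to light.* The forms are not available and spontaneous reports were possible. The documents support only that no systematic collection is described.
- *That week 2 was the only contact.* Weekly emails, a second questionnaire and a final visit are also described. Week 2 is the only data collection described within the four weeks.
- *That the injury exclusion shows the authors feared harm.* No reason is given for it. Avoiding confounding of a head-posture outcome would explain it equally well.
- *That the seven losses were caused by harm.* Nothing says so. Without arm or reason, it can be neither shown nor excluded.
- *That collecting harms would have allowed a proper comparison of arms.* The power figures say otherwise.

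The adherence argument is weaker than it looks. The lowest accepted band still allows up to half of sessions to be missed for reasons not described as collected, and it cannot speak for anyone who left without answering. The core of the point also survives the objection from brevity: the section on questionnaires and follow-up gives the purpose of every data collection, none is harm, and neither the analysis nor the results supplies it.

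**Conclusion.** The point holds as a gap in what the trial is described as collecting, analysing and reporting. Following the plan as written gives no systematic information on harm in any of the four arms, for a home programme assigned to 39 people, and leaves 7 of 79 (8.9%) unaccounted for by arm or reason. It does not touch the CVA analysis. Its consequence is that no safety conclusion, favourable or unfavourable, can be drawn: even the modest zero-event limits of 7.4% (39 people) or 14.6% (19 people) are unavailable when no enquiry is described.

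This rests on two assumptions: that the questionnaires contained what their stated purpose says and no more, and that the results as given are complete on this matter. If the forms did carry a symptom or injury item, reporting the answers would meet most of the concern, except that controls are not described as receiving either form.

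**What to change.** **For the plan, or any repeat of it.** Add one short item to the existing mid- and post-study questionnaires: any new or worse neck, shoulder, head or back symptoms or injury since the last contact, and whether sessions were missed because of them. Put the same wording to controls, by email at week 2 and at the follow-up visit. Make the week-2 answers available to the investigator; any clinical response is left to the investigators. Report counts by arm, and withdrawals by arm and reason, descriptively and without a powered comparison.

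**For the completed trial.** Report the seven non-completers by arm and reason. State that harms were not systematically assessed and that no safety conclusion can be drawn. If the forms did contain a harms item, report its results by arm instead.

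**Cost.** A few lines on forms already in use, one email to the control arm and one extra table. The downside is that minor soreness will be reported and, because participants were not blinded, self-report may raise counts in the active arms. The report should say so next to the counts.

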### **Statistical Analysis**

Data were analyzed using IBM SPSS version 28 for Windows (SPSS Inc., Chicago, IL, USA) and reported with mean and standard deviation. Descriptive participant characteristics by group were analyzed with a one-way ANOVA. Paired samples *t*-tests were used to assess within-group differences in means between pre- and post-intervention CVA measures. Between-group comparisons of post-intervention mean CVA change were analyzed with a one-way ANOVA. Levene's test was utilized to assess equality of error variance. Gabriel's test was selected for post-hoc comparisons. The significance level was set at  $p < 0.05$ .

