## **Study Protocol, Statistical Analysis, and Results**

### **Study Protocol**

Participants who responded to invitations to voluntarily participate completed the Physical Activity Readiness Questionnaire (PAR-Q+) (Warburton et al. 2011), followed by a questionnaire to rate their current stage of change (SOC) from the Transtheoretical Model adapted to assess exercise/postural modification behavior change. On this questionnaire, participants also responded to a yes/no question regarding if they have had a recent injury to their head, shoulders, or spine; or have ever been diagnosed with a pathology related to their cervical/thoracic spine or extremities, as part of exclusion criteria for the study. Participants then underwent a head posture screening with the use of photogrammetry. Screening was performed by the primary investigator who is a licensed physical therapist in the Liberty University Biomechanics & Motion Analysis Laboratory.

Participants were asked to arrive at the lab wearing either a tank top or t-shirt, as well as to have their hair tied back if necessary. Height and weight were measured using a digital scale (Health-o-meter Professional, model 500KL, McCook, IL). Participants were instructed to sit comfortably on a stool with hands resting approximately two-thirds down their thighs with palms supinated and feet flat on the ground with hips and knees at 90 degrees (Richards et al. 2016); and to look straight ahead at an opposite wall in the laboratory (Kim et al. 2016). A digital camera (Canon Powershot, model SX540, Tokyo, Japan) was mounted and leveled on a tripod (Manfrotto, model 055, Cassola, IT) and placed three meters away from the subject (Ruivo et al. 2014). Two photographs were taken of participant's posture (Kim et al. 2016). Immediately after data capture, image files were uploaded into Kinovea video analysis software (version 8.15) for CVA assessment. On each image file, the PI assessed participant CVA by measuring the angle

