## **Results**

The trial was completed by 72 participants (51 females, 21 males) with a mean age: 20.17 (SD:  $\pm 2.25$  years); mean height: 167.34 (SD:  $\pm 8.25$  cm); and mean weight: 70.31 (SD:  $\pm 14.61$  kg). All participants reported SOC self-rating  $\geq 3/5$ . Pre-intervention analysis revealed no significant difference ( $p > 0.05$ ) in participant age or anthropometric characteristics between groups. No significant between-group differences ( $p > 0.05$ ) in baseline CVA were present. Within-group comparisons of pre- vs post-intervention CVA outcomes revealed a significantly ( $p < 0.05$ ) greater post-intervention CVA in the PE, SMRS, SMRSS, and CG. Post-hoc comparisons indicated post-intervention mean CVA change in the SMRS group: 3.8 (SD:  $\pm 3.3$  deg.); and the SMRSS group: 4.4 (SD:  $\pm 3.1$  deg.); was significantly greater ( $p < 0.01$ ) than the CG: 0.8 (SD:  $\pm 1.7$  deg.). All participants in the SMRS and SMRSS groups reported intervention adherence as moderately consistent (50-75% sessions performed) or higher on both the mid- and post-study questionnaire. 91% of the PE group reported intervention adherence as moderately consistent (50-75% adherence to guidelines) or higher on the mid-study questionnaire. 96% of the PE group reported intervention adherence as moderately consistent or higher on the post-study questionnaire.

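### CVA change is compared between groups without baseline CVA: this causes no bias, but one labelled post hoc ANCOVA would be a nearly free check, with a gain that the documents cannot fix

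*Combined protocol and SAP*

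**What the plan says.** The between-group method is in the Statistical Analysis section: "Between-group comparisons of post-intervention mean CVA change were analyzed with a one-way ANOVA". It continues: "Levene's test was utilized to assess equality of error variance", and "Gabriel's test was selected for post-hoc comparisons". The threshold is 0.05. No covariate, adjusted model or sensitivity analysis appears anywhere in the document.

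Baseline CVA is available for everyone. Under Study Protocol, "Participants then underwent a head posture screening with the use of photogrammetry", and for each person "the CVA was derived by taking the mean of two CVA measurements that were assessed on the captured photographs". A CVA of 53 degrees or less was an entry condition. The Intervention Groups section places group-specific contact after the baseline assessment.

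Results deals with baseline only through a test: "No significant between-group differences" in baseline CVA (p > 0.05). It gives CVA change as 3.8 (SD 3.3) in SMRS, 4.4 (SD 3.1) in SMRSS and 0.8 (SD 1.7) in CG, with p < 0.01 for each exercise group against CG.

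**The concern.** Analysing change assumes that each extra degree of baseline CVA goes with exactly one extra degree afterwards. If the true slope is below 1, as it is when people with the lowest angles tend to gain most, change still carries baseline variation that a covariate would remove. The contrasts are then less precise than the data allow, and a chance difference in baseline moves the estimates.

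The non-significant baseline test does not answer this. It adjusts no estimate, and without baseline means and SDs a reader cannot judge how large an imbalance remains.

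What is at stake is the width of the intervals and some movement in the point estimates. The unadjusted standard errors already allow for chance imbalance, so it is not a further hidden error.

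**Working it through.** **1. The reported result.** The only stated figure that bears on this is p < 0.01 for the two exercise-CG contrasts. The document gives neither completers per arm nor the PE change SD. Assume 18 per arm (72/4) and a PE SD of 2.5.

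- Pooled variance = (2.5² + 3.3² + 3.1² + 1.7²)/4 = 29.64/4 = 7.41, so s = 2.72.
- Gabriel's statistic = difference / [s(1/√36 + 1/√36)] = difference/0.907.
- SMRS-CG: 3.0/0.907 = 3.31, p = 0.009. SMRSS-CG: 3.6/0.907 = 3.97, p = 0.001 (studentized maximum modulus, 6 contrasts, 68 df).

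Over 15 assumed combinations of arm sizes and PE SD (1.7, 2.5, 3.3), SMRSS-CG gives p from 0.0004 to 0.0085. SMRS-CG gives 0.003 to 0.039 and is below 0.01 in 9 of 15. The reported result is compatible with the figures given but cannot be uniquely reproduced.

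**2. Cost of the covariate.** It takes one degree of freedom and an average variance factor of 1 + 1/(72 − 4 − 2) = 1.015, or about 0.8% in interval width. It pays for itself once the correlation between change and baseline exceeds about 0.12 in absolute value.

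**3. Illustrative gain.** Let S be the baseline SD and D an arm's change SD. With equal pre and post SDs, the arm's slope is ρ = 1 − D²/(2S²). The common slope b is the mean over four arms, with PE set to the SMRS value or to the CG value. Residual variance in an arm is S²(1 − 2bρ + b²). Net variance ratio = 1.015 × (sum of the two residual variances)/(sum of the two D²).

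| S (deg) | ρ: SMRS, SMRSS, CG | b | SMRS-CG | SMRSS-CG | SMRSS-SMRS |
|---|---|---|---|---|---|
| 3 | 0.395, 0.466, 0.839 | 0.524 to 0.635 | 0.832, 0.821 | 0.863, 0.839 | 0.734, 0.763 |
| 4 | 0.660, 0.700, 0.910 | 0.732 to 0.795 | 0.912, 0.906 | 0.930, 0.916 | 0.857, 0.874 |
| 5 | 0.782, 0.808, 0.942 | 0.829 to 0.869 | 0.949, 0.945 | 0.960, 0.952 | 0.914, 0.925 |

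In each pair the first figure has PE like SMRS and the second PE like CG. The ratios run from 0.734 to 0.960, a fall in variance of 4 to 27%, or 2 to 14% in interval width (√0.960 = 0.98; √0.734 = 0.86).

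**4. Outside that illustration.** If the post SD is 0.8 times a baseline SD of 3, the same method gives ratios of 0.52 to 0.63. If the slope is 1 (post variance equals baseline variance plus change variance), the residual ratio is 1 and the net ratio 1.015.

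**5. Entry limit.** In a simulation with SD 5 before and after and a cut at the mean, the slope was 0.60 both before and after the cut (0.80 and 0.80 at the higher correlation). Baseline SD fell from 5 to 3.0. The share of change variance explained by baseline fell from 0.20 to 0.08 (0.10 to 0.04 at the higher correlation).

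**6. Would conclusions move?** The baseline difference between two arms has SE S√(2/18). A one-SE imbalance shifts a contrast by (1 − b) times that: at S = 3 and b = 0.524, 0.476 × 1.00 = 0.48 deg. Take this one scenario (PE like SMRS) and the unadjusted Welch SEs of 0.875, 0.833 and 1.067, with each shift in the direction that tests the conclusion:

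- SMRS-CG: (3.0 − 0.48)/(0.875√0.832) = 2.52/0.798 = 3.16. On about 25 df, p is below 0.005, and six times that is below 0.03.
- SMRSS-CG: 3.12/(0.833√0.863) = 3.12/0.774 = 4.03.
- SMRSS-SMRS: (0.6 + 0.48)/(1.067√0.734) = 1.08/0.914 = 1.18, inconclusive.

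**The case against.** The strongest reply is that nothing is wrong. ANOVA on change is an accepted analysis of a randomised trial, the main conclusions would probably survive, the gain may be nil, and choosing another model once results are known is a matter of preference. Most of this stands, which is why the point is an optional addition. It does not remove the case for one extra model on data already held, at a cost of about 1.5% in variance.

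The inputs are also weak, and that stands too. Baseline SD and arm sizes are assumed. Eighteen PE completers does not fit the reported adherence: no fraction with a denominator of 20 or less rounds to 96%, and only 10 of 11 rounds to 91%. Unequal variance (3.3² against 1.7², a ratio of 3.8) is a separate matter, on which a Games-Howell check would be at least as informative.

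Four stronger readings are tempting and not supported:

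- A reader might infer that the reported comparison is biased. Omitting a baseline covariate does not bias a randomised contrast.
- A reader might infer that the 53-degree limit pushes the slope towards 1 and removes the gain. Selecting on the covariate leaves a linear slope unchanged; it narrows baseline spread and so may shrink the gain.
- A reader might take equal pre and post SDs as the most favourable case. Step 4 shows that it is not a bound.
- A reader might expect the ANCOVA to show whether effects vary with baseline. A common-slope model adjusts for imbalance; varying effects would need an interaction term.

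**Conclusion.** The point holds as a low-cost improvement to consider. The group comparison ignores a baseline value held on every participant. That costs no validity, but it may cost precision and it leaves chance imbalance unadjusted.

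The size cannot be fixed from the document. The 4 to 27% fall in contrast variance rests on 18 per arm, equal pre and post SDs, a baseline SD of 3 to 5 degrees, and a PE correlation set to the SMRS or the CG value. It is an illustration, not a range that contains the answer. Adjusted intervals quoted to a decimal would be false precision, since the estimates can move as well as the standard errors.

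The SMRS-CG and SMRSS-CG conclusions at the 0.05 level are unlikely to change. The 0.6-degree SMRSS-SMRS difference stays inconclusive in the scenario worked above. PE contrasts cannot be sized. The adjustment does nothing about the 7 of 79 participants who did not complete.

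**What to change.** Keep the reported ANOVA and Gabriel comparisons as the main result. Beside them, labelled post hoc because results are already known, add one ANCOVA of post-intervention CVA on group with baseline CVA as covariate.

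- Use heteroscedasticity-robust standard errors, given change SDs of 3.3 and 3.1 against 1.7 and no reported Levene result.
- Report all six pairwise adjusted differences with 95% CIs under a named family-wise adjustment such as Holm or Sidak. Sidak has the convenience that the intervals match the tests.
- Report baseline and post-intervention means and SDs, the pre-post correlation and the number of completers by arm, so that readers can see what the adjustment did.

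The cost is one degree of freedom and one model on existing data. The result may show no gain, or a loss of about 1.5% in variance (0.8% in interval width), and should be reported whichever way it falls.
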